## 6. GENERAL STATISTICAL CONSIDERATIONS

### 6.1. Sample Size

The sample size will be approximately 105 subjects, 35 per arm, barring early stopping. The original accrual rate is assumed to increase with time such that approximately 9-12 subjects will accrue in the first 3 months and a total of 41 to 55 subjects will accrue by 6 months with the remainder accruing by 60 weeks. Therefore, in addition to monitoring toxicity and progression, the accrual rate will be monitored.

The operating characteristics for the Bayesian Beta prior/schedule-administration adaptive design are given in protocol **Error! Reference source not found.**

### 6.2. Randomization and Stratification

Stratification and randomization will be performed by IVRS, an Interactive Voice Response System, to ensure a 1:1:1 central randomization. Subjects will be stratified at randomization by:

- Relapsed versus refractory to their last purine-analog or bendamustine based treatment regimen [relapsed/refractory as defined per the iwCLL guidelines for diagnosis and treatment of CLL (Hallek, 2008). If a subject has had prior purine-analog based and bendamustine based regimen, the stratification will be based on the subject's status post most recent regimen.
- Age < 65 years of age versus  $\geq$  65 years of age

### 6.3. Randomized Bayesian Design

This study will be conducted using a randomized Bayesian schedule-administration design that jointly models toxicity/response outcomes using an extension methods developed in (Bekele, 2004) (Bekele, 2005) (Bekele, 2008a) (Bekele, 2008b). Schedule-administration (or treatment strategy) designs differ from standard treatment designs in that the object of interest is not to determine if one treatment is superior to an alternative treatment, but to determine if a particular treatment administration schedule is superior to other competing schedules. In the context of the current design Celgene is interested in evaluating whether various intra-subject dose-escalation schemes are safe and effective while monitoring safety and efficacy (futility). Specifically, while treatment starts at various doses ranging from 5 mg/daily to 15 mg/daily, the goal is to perform intra-subject dose escalation (every 28 days as tolerated) until a maximum dose of 25 mg/daily is achieved. The decision to escalate is based on how well the subject tolerates the lower dose levels. While these dose escalations are taking place, toxicity and the progression rate will be monitored.

[REDACTED]

[REDACTED]

Operationally, the study will proceed as follows: Subjects will be randomized to one of the three treatment arms. The first interim analysis (toxicity only) will be performed once 18 subjects have completed one 28-day cycle. Subsequent interim analyses will occur at 13-week intervals to monitor both combined toxicity and progression rates.

[REDACTED]

- [REDACTED]
- [REDACTED]
- [REDACTED]
- [REDACTED]

If a treatment arm is dropped then all new subjects will be randomized equally into the remaining arms.

[REDACTED]

## 6.4. Analysis Populations

### 6.4.1. Safety Population

The safety population is defined as all randomized subjects who receive at least 1 dose of the study drug.

Drug exposure and all safety analyses (including adverse events, labs, and deaths) will be based on the safety population. Subjects will be analyzed according to the initial treatment actually received.

### 6.4.2. Intent-to-Treat (ITT) Population

The Intent-to-Treat (ITT) population is defined as all subjects who are randomized, independent of whether they received study drug or not. The ITT population will be used for the -efficacy analysis.

Subject disposition, demographics, baseline characteristics, and all efficacy analyses will be based on the ITT population unless specified otherwise. All subjects in the ITT population will be analyzed according to the treatment they were randomized to receive and not according to what they actually received, if different.

## 6.5. Reporting Conventions

The algorithms, imputations, and conventions that will generally apply to programmed manipulations of the data for summary tabulations and individual subject data listings are described in this section.

Summary tables, listings, and any supportive SAS output will include a “footer” of explanatory notes that will indicate, at a minimum, the:

- Program source (e.g, SAS program name, including the path, that generates the output) and
- Data extraction date (e.g, the database lock date).

The purpose of the data extraction date is to link the output to a final database, either active or archived, that is write-protected for replication and future reference. An output date will also appear on each output page and will indicate the date the output was generated by the analysis program.

### 6.5.1. Tables

Data in tables will be summarized for each of the treatment arms and overall subjects when appropriate. Tables will contain the number of subjects in the analysis population for each column and the total number. Presentations will be summarized by cycle if applicable. In selected presentations the event or assessment indicating the most severe event by NCI CTCAE

toxicity grade or most abnormal assessment (analysis of the “worst” case) for each subject over the course of the study will be summarized.

Time points in the summaries will reflect the time periods described in the protocol and CRF, such as ‘Baseline’, ‘Cycle 1 Day 1’, ‘Cycle 2 Day 1’, etc.

Age will be displayed in years and relative days (e.g., study days) will be displayed in days. Dosing exposure and treatment durations will also be displayed in days; all other time intervals will be presented in weeks.

The following descriptive statistics will be displayed for each quantitative variable: n, mean, median, standard deviation (SDev), minimum, and maximum.

Qualitative variables will be presented as category frequencies and percentages. The denominator for calculating percentages will be either the number of subjects in the analysis population or the number of non-missing observations in the treatment arm for the particular variable presented. Visit windows will not be used in the data analyses. The cycle number recorded on the CRF, if available, will be used to mark the data collection time points. Actual visit or assessment dates will be used to calculate intervals of time.

If a given table template specifies the summarization of a given qualitative CRF variable and no such response appears on a CRF for any of the subjects in the study population appropriate to that table, the entire row may be deleted from the summary rather than present a row of zeroes for that response.

### 6.5.2. Listings

Data listings will be sorted by treatment arm (for unblinded analysis), subject number, and cycle number, if applicable.

### 6.5.3. Dates

Dates will be displayed in ddmmyyyy format (e.g., 30JUN2002).

Calculations using dates will adhere to the following conventions:

- Study days after the start day of study drug will be calculated as the difference between the date of interest and the first date of dosing of study medication (e.g, lenalidomide) plus 1 day. The generalized calculation algorithm for relative day:  $STUDY\ DAY = [(TARGET\ DATE - DSTART) + 1]$  where DSTART = the start day of study drug]. Note that Study Day 1 is the first day of treatment of study drug. For study days before the start day of study drug the algorithm is:  $STUDY\ DAY = (TARGET\ DATE - DSTART)$ . Negative study days are reflective of observations obtained during the baseline/screening period.
- Age (expressed in days) is calculated:  $AGE = Informed\ Consent\ Date - DTBIRTH + 1$ . In practice, age will be converted to years by dividing the difference by 365.25 days, then truncating to a whole number.
- The conversion between weeks and months can be performed by using the following conversion formula (without truncation):  $MONTHS = WEEKS * 7/30.4$ .

- Partial dates will be reported as recorded in the data listings. There will be no imputation for missing parts of dates, unless for the purpose of
  1. determining treatment emergent AEs when the AE start date is partial, or
  2. differentiating medication taken prior to the study treatment from concomitant medication taken during the study when the medication start date is partial.

The conventions for imputing partial dates for such purposes are as follows:

1. The onset date has year but both month and day missing
  - If the year of onset = year of first study drug dose, then the onset date = First study drug dose date.
  - If the year of onset < year of first study drug dose, then the onset month = 12 and the onset day=last day of the month.
  - If the year of onset > year of first study drug dose, then the onset month = 1 and the onset day=1.
2. The onset date has year and month but day missing
  - If the year and month of onset = year and month of first study drug dose, then the onset date = first study drug dose date.
  - If the year of onset < year of first study drug dose, or the year of onset = year of first study drug dose but the month of onset < the month of first study drug dose, then the onset day = last day of the month.
  - If the year of onset > year of first study drug dose, or the year of onset = year of first study drug dose but the month of onset > month of first study drug dose, then the onset day = first day of the month.

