CC-5013-CLL-009 is a phase 2, multi-center, randomized, double-blind, parallel-group adaptive design study that will evaluate the safety and efficacy of different lenalidomide dose regimens administered orally. All regimens use a stepwise dose escalation scheme with three different initial ascending starting dose of 5 mg daily, 10 mg daily and 15 mg daily and then escalating in a stepwise manner every 28 days to reach a maximum dose of 25 mg daily based on subject tolerability. Approximately 105 subjects will be enrolled. Eligible subjects must have B-cell CLL that has relapsed after or is refractory to at least one prior CLL treatment regimen. At least one of the prior treatments must have included a purine-analog or bendamustine based treatment regimen. Subjects must have active disease per the iwCLL Guidelines for the diagnosis and treatment of CLL (Hallek, 2008).

At the time of randomization, study subjects will be stratified by the following criteria:

- Relapsed vs. refractory to their last purine-analog or bendamustine based treatment regimen [relapsed/refractory as defined per the iwCLL guidelines for diagnosis and treatment of CLL (Hallek, 2008)]. If subject has received both, the status post most recent purine-analog or bendamustine regimen will be used for stratification.
- Age < 65 years of age vs. \ge 65 years of age

Screening

Subjects will sign informed consent prior to undergoing any study-related procedures. Screening assessments for protocol eligibility will be performed within 28 days prior to initiating study drug as outlined in Table 2.

During screening all subjects will have the following assessments / samples collected:

- Vital signs, including height and weight
- Pregnancy testing as specified in Appendix 21.9
- Pregnancy and risk counseling as specified in Appendix 21.9
- Assessment of ECOG performance score
- Assessments of constitutional symptoms
- Physical examination to assess the lymph nodes, spleen and liver
- Clinical staging using Rai and /or Binet as defined per the iwCLL guidelines for diagnosis and treatment of CLL (Hallek, 2008) in Appendix 21.4
- 12-lead ECG
- Peripheral blood smear, bone marrow aspirate and bone marrow biopsy (reference samples) for central pathology reviewer (local pathology results will also be captured on the eCRFs).
- Peripheral blood for disease confirmation by immunophenotyping per Hallek, 2008.

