- t. AEs will be reported from the time informed consent is signed to 30 days post last dose of study drug. AEs that lead to study discontinuation should be followed until resolution or stabilization. For subjects who discontinue study treatment but continue to be followed every 28 days until PD or new CLL therapy, AEs will be reported until 30 days post last dose of study drug or until study discontinuation, whichever occurs last. SAEs will be reported from time informed consent form is signed to 30 days post last dose of study drug. SAEs will be reported at any time post last dose of study drug if it is considered related to study drug.
- u. Second primary malignancies will be monitored as events of interest and must be reported as serious adverse events regardless of the treatment arm the subject is in. This includes any second primary malignancy, regardless of causal relationship to study drug, occurring at any time for the duration of the study, from the time of signing the informed consent up to and including the survival follow up period. Subjects will be followed until 80% of the subjects have progressed or died or up to five years after the last subject was randomized, whichever occurs later. Events of second primary malignancy are to be reported using the SAE report form and must be considered an "Important Medical Event" even if no other serious criteria apply; these events must also be documented in the appropriate page(s) of the CRF and subject's source documents. Documentation on the diagnosis of the second primary malignancy must be provided at the time of reporting as a serious adverse event (e.g., any confirmatory histology or cytology results, X-rays, CT scans, etc.).
- v. Investigators to provide assessment of CR, CRi, nPR, PR, SD, and PD based on laboratory, physical exam, assessment of constitutional symptoms and if appropriate CT scan findings (CT scans are to be performed at baseline and to confirm PR or CR/CRi). For confirmed PR, nPR or CR/CRi, response must be maintained for ≥ 8 weeks as per the iwCLL guidelines for the diagnosis and treatment of CLL (Hallek, 2008) Tumor response will be assessed according to

- the iwCLL guidelines (Hallek, 2008) for the diagnosis and treatment of CLL (Hallek, 2008), including CR, CRi, nPR, PR, SD, and PD. Evaluation of response will be performed after 3 cycles of therapy and every 4 weeks thereafter.

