### 12.1. Adverse Events

The adverse events of Neutropenia, Anemia and Thrombocytopenia will be analyzed according to the grading system as recommended by the IWCLL guidelines for the diagnosis and treatment of CLL (Hallek, 2008).

The adverse event of Tumor Lysis Syndrome (TLS) will be analyzed according to the grading system as recommended by Cairo-Bishop grading system.

Treatment emergent adverse events (AEs) will be summarized by treatment arm and overall. A treatment emergent adverse event is defined as any AE occurring or worsening on or after the first treatment of any study drug, and within 30 days after the last dose of the last study drug received. Adverse events will be presented in descending order of frequency (for all subjects) by SOC, and then within each SOC, by decreasing order of preferred term. Adverse events are documented on the CRF together with their severity, according to the NCI CTCAE version 3.0 or higher, also referred to as NCI toxicity grading. For the categorization of the adverse events, the MedDRA® dictionary (version 15.0) will be used.

AE frequency will be tabulated by body system, MedDRA preferred term for each treatment regimen during the Treatment Phase as well as for the Follow-up Phase when appropriate. In the by-subject analysis, a subject having the same event more than once will be counted only once and by the greatest severity. AEs will be summarized by worst NCI CTCAE version 3.0 grade. In the case that the AEs or event frequencies are judged to be clinically important, an exact test may be used to analyze the difference between the treatment arms. Events of interest will also be summarized by treatment cycles.

AEs leading to death or to discontinuation from treatment, events classified as NCI CTCAE version 3.0 Grade 3, 4, and 4 AEs, treatment-related events, serious adverse events (SAEs) and events of interest (including second primary malignancies) will be summarized separately.

Individual AE listings by subject will be provided.

As an exploratory analysis, AEs will be summarized by treatment arm and by subgroup (i.e., relapse vs. refractory, age <65 vs. age ≥65, lines of prior CLL treatment, gender).

Adverse events (AE) will be classified using the Medical Dictionary for Regulatory Activities (MedDRA) classification system. The severity of the toxicities will be graded according to the NCI CTCAE version 3.0 whenever possible.

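### When the known parts of an AE's onset date match first dose, SAP 6.5.3 imputes the first-dose date without checking the end date, so an AE known to have ended before dosing can be counted as treatment-emergent

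*SAP*

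**What the plan says.** SAP 6.5.3 leaves partial dates as recorded, with two exceptions. One is "determining treatment emergent AEs when the AE start date is partial, or" and the other is separating prior from concomitant medication.

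For these purposes the imputation depends only on how the known parts of the onset date compare with first dose:

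- Day missing, same month and year: if they equal the "year and month of first study drug dose, then the onset date = first study drug dose date".
- Day and month missing, same year: "If the year of onset = year of first study drug dose, then the onset date = First study drug dose date".
- Day missing, earlier month of the same year: if "the month of onset < the month of first study drug dose, then the onset day = last day of the month", which places the onset before dosing. An earlier year is also placed before dosing.
- Later month or year: first day of that month or year.

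SAP 12.1 defines a treatment-emergent AE as "any AE occurring or worsening on or after the first treatment of any study drug", up to 30 days after the last dose. Neither section mentions the AE end date.

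Protocol Table 2, footnote t, starts collection before dosing: "AEs will be reported from the time informed consent is signed to 30 days post last dose of study drug". The Synopsis sets the length of that period: "Screening assessments for protocol eligibility will be performed within 28 days prior to initiating study drug".

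**The concern.** An AE can begin and end between consent and first dose and still be in the database. If its onset day is missing and its month and year match first dose, the rule dates it to the day of first dose, even when the recorded end date shows that it was already over. The imputed record then contradicts itself, because the onset falls after the end, and the event is flagged as treatment-emergent.

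The primary endpoint is safety: the type, frequency and severity of AEs and their relationship to lenalidomide (Protocol 7.1, SAP 5.2). SAP 12.1 reports it largely through tables of treatment-emergent events, so a wrong flag there adds an event to an arm's count that the drug could not have caused.

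The same imputation applies to medications. One that was stopped before dosing can be given a start date on the day of first dose.

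**Working it through.** **Step 1: apply the rule as written.** Take a hypothetical first dose on 20JUN2011.

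| Recorded onset | Recorded end | Imputed onset | Treatment-emergent under SAP | With an end-date check |
|---|---|---|---|---|
| `--JUN2011` | 12JUN2011 | 20JUN2011 | Yes | No |
| `----2011` | 12JUN2011 | 20JUN2011 | Yes | No |
| `--MAY2011` | 12JUN2011 | 31MAY2011 | No | No |
| `--JUN2011` | ongoing | 20JUN2011 | Yes | Yes |

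In the first two rows the imputed onset is 20 − 12 = 8 days after the event ended. The third row shows that an earlier-month onset is unaffected. The fourth shows that an end-date check keeps the cautious default where timing really is unknown.

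**Step 2: how much of the screening period is exposed.** The plan gives no figure for this, so the following is a model and not an event count.

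- From the Protocol: a screening window of 28 days before first dose.
- Assumed: first-dose day uniform over a 30-day month (or a 365-day year), onset uniform over the eligible days of the window, and a fixed event duration of L days.

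Let onset be k days before first dose. The event ends L days later, so it is over before dosing only if k runs from L + 1 to 28. Onset falls in the first-dose month when the day of the month of first dose exceeds k, which has probability (30 − k)/30. Averaging over k:

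- share in the same month = 1 − mean(k)/30
- share in the same year = 1 − mean(k)/365

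| L (days) | k runs over | mean(k) | Same month (day missing) | Same year (year only known) |
|---|---|---|---|---|
| 0 (limit) | 1 to 28 | 14.5 | 1 − 14.5/30 = 52% | 1 − 14.5/365 = 96% |
| 7 | 8 to 28 | 18 | 1 − 18/30 = 40% | 1 − 18/365 = 95% |
| 14 | 15 to 28 | 21.5 | 1 − 21.5/30 = 28% | 1 − 21.5/365 = 94% |

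Counting over every first-dose date in the real calendar of 2011 gives 52.3% and 96.0% for the L = 0 row, so the 30-day simplification does no harm. For one subject the same-month share of the window runs from 0% to 100%, depending on the day of first dose.

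**Step 3: effect of one misclassified event.** With the planned 35 subjects per arm, one extra subject with a given term changes its incidence by 1/35 = 2.9 percentage points. SAP 12.1 counts a subject once per event, so the change is zero if the same subject also has that event on treatment. The 2.9 points is therefore a maximum per case.

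**The case against.** The strongest reply is that the definition in SAP 12.1 already excludes these events. An AE that ended before dosing neither occurs nor worsens on or after first dose, and imputation is only a device for uncertain starts. That is a fair account of the intent. But SAP 6.5.3 makes the imputed onset the means of setting the flag and states no exception, so a programmer who follows it literally will count the event.

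A second reply is that defaulting to first dose is conservative. That stands where the end date is missing, or on or after first dose. It does not stand where the end date settles the question.

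A third reply is that the affected set is narrow, and this stands. The event must start after consent, because Protocol Appendix 21.1 does not record unchanged pre-existing conditions as AEs. It must have a partial onset that matches first dose. It must also have an end date precise enough to prove resolution before dosing. Appendix 21.1 requires stop dates explicitly only for serious events; for other AEs their collection is an assumption. Partial dates are also listed as recorded, so such cases can be seen in the listings.

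A reader might infer four stronger points that the documents do not support:

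- *Every AE with a missing onset day is moved to first dose.* Only those matching the month and year of first dose are, or the year where only the year is known.
- *About half of resolved screening AEs with a missing day are misclassified.* The 52% is the share of all screening days that fall in the first-dose month. Events that resolve before dosing must start earlier, so 52% is an upper limit.
- *Treatment emergence is itself the primary endpoint.* It is the rule by which SAP 12.1 tabulates the endpoint.
- *A medication stopped before dosing becomes concomitant.* SAP 10 defines prior as started before study treatment and concomitant as started after the first dose. A start imputed to the day of first dose loses prior status, but its class is then left unclear.

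**Conclusion.** The defect is real and limited. Followed as written, SAP 6.5.3 can give an AE an onset later than its recorded end and place a pre-dose event in the treatment-emergent tables. This is a stated rule that yields a wrong result, not merely a missing detail.

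The number of affected events cannot be derived from the documents and is probably small. The error tends to overstate treatment-emergent counts. The rule is the same in all arms, and nothing suggests a difference between them, so there is no basis for claiming a biased comparison of starting doses.

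The exposure shares rest on uniform dosing days and onsets and on assumed durations. The per-case maximum rests on the planned arm size. The finding itself needs only a recorded end date that shows resolution before first dose.

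**What to change.** Add to SAP 6.5.3, before the tables are run:

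> Imputation to the first-dose date applies only if the end date is missing, the event is ongoing, or the end date does not show that the event ended before first dose. If the recorded end date, full or partial, shows that the event ended before first dose, the event is not treatment-emergent. An imputed onset may not be later than the end date. The same check applies to medications: one stopped before first dose is prior, not concomitant.

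A partial end date is enough when its known parts settle the matter, for example an end in a month before the month of first dose. Where it does not settle the matter, the present default remains.

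The cost is this short addition and about one line of code. No new data are needed if stop dates are already on the AE form.
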